Theoretical framework of health service utilization. The Behavioral Model for Vulnerable Populations is commonly used to explain health seeking behaviors and predict health outcomes of vulnerable populations, including PWID.⁴⁶ According to this model, predisposing, enabling, and need components will predict BMT utilization, which in turn will predict health outcomes. The model is useful in health services research, because factors that contribute to vulnerability may impede service utilization and should be considered as predisposing or enabling factors. Figure 1 outlines the components of the model that are relevant to this proposal. As illustrated, our target population is likely to have many predisposing factors that affect health behaviors and outcomes, including minority race/ethnicity, criminal behavior, substance use, and mental illness. Enabling factors are resources that facilitate OUD treatment, including insurance, transportation, ability to negotiate complex systems, and access to BMT providers. Need factors are determined by individuals' perceived and evaluated health care needs. In an environment with adequate insurance (i.e., Medicaid), transportation (i.e., public transportation), and access to BMT providers (see section D.3), our structural intervention of onsite treatment, is predicted to increase BMT initiation and engagement. The enabling factor of onsite treatment will allow participants to initiate BMT when they are ready, instead of finding a provider, scheduling and waiting for an appointment, completing paperwork, and then waiting for assessment – potentially while in withdrawal. Of previously described barriers to BMT, health system fragmentation, waiting times, and fear of discrimination in medical settings can be addressed.

Principal Investigator: [name]

through onsite treatment.⁴⁵ This enabling factor will help participants meet their perceived health needs (i.e., need for OUD treatment), which will have a positive effect on health outcomes.

[figure not shown]

Figure 1. Theoretical Framework

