Overview of study approach. In a 24 week RCT based in a large urban area with high rates of OUD and HIV, we will recruit 250 out-of-treatment opioid users from SEPs and randomize 1:1 to onsite BMT initiation (**O-BMT**) or enhanced referral. Over two weeks, participants in the O-BMT arm will see a buprenorphine provider twice, receive prescriptions of medication, and then their care will be transferred to a community health center (CHC) for maintenance BMT. In the control arm, participants will receive enhanced referral to a CHC for initiation and maintenance BMT. We will assess participants with urine drug tests, questionnaires, and medical record review studying treatment engagement, treatment outcomes (opioid use, HIV risk behaviors) and programmatic service utilization in order to establish effectiveness and costs. We will also assess buprenorphine diversion using electronic monitors, urine drug testing, and sequential surveys.

Setting. A. New York Harm Reduction Educators (NYRHE) is the largest harm reduction agency in New York City with over 35 staff members and serving over 5000 clients annually. At two community-based offices and 11 street-side locations, NYHRE provides participants with syringe exchange; referral for medical, dental and addiction treatment; and other supportive services. The majority of NYHRE's clients are Hispanic or black, male, 40-49 years old, and PWID. Diverse staff members (case managers, outreach workers, and syringe exchange staff) have received training on BMT. O-BMT will be offered at community-based offices only.

B. Washington Heights CORNER Project (WHCP) is another harm reduction agency situated in an area highly affected by OUD and HIV. At its community-based office, WHCP provides clients with syringe exchange; referrals for medical, dental, or addiction treatment; and other supportive services. WHCP serves over 1500 clients annually with similar characteristics as NYHRE. WHCP staff members have received training on BMT.

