Medical Records: We will extract medical record data from the CHC, including prescription and visit information to assess *treatment engagement* and *retention in care*. Prescription data will include information both from the electronic medical record (prescriptions) and the NY Prescription Drug Monitoring Program (medications dispensed). As mandated by law, the later source includes all controlled substances dispensed by all pharmacies in New York State. Prescription data will include medication name, strength, directions, number of pills, number of refills, date of prescription, prescriber, and date medication was filled. Visit data will include date of visit, and provider. If participants request referral to a different site for BMT or are transferred to an alternative form of OUD treatment (e.g., methadone maintenance), we will request medical records using the signed, HIPAA-compliant release for medical records.

Urine Drug Testing: All research visits will include urine collection, which will be tested for buprenorphine, opiates, oxycodone, methadone, cocaine, methamphetamine and benzodiazepines.

Table 2. Timing and delivery of intervention and study measures

Measure	Study Instrument	Assessment Period (week)									
		0	1	2	4	6	8	1	2	2	4
Urine Drug Tests											
Opioid use	Urine Drug Testing	x	x	x	x	x	x	x	x	x	x
Questionnaires											
Sociodemographic information	BHIVES Study ⁶⁶	x									
HIV Risk Behaviors	RBS ⁸⁶	x		x					x	x	
Self-reported drug use	Addiction Severity Index ⁸⁷	x			x		x	x	x	x	
Depressive Symptoms	CES-D ⁸⁸	x		x				x	x	x	
Self-efficacy	DTCQ-8 ⁸⁹	x		x				x	x	x	
Quality of Life	EQ-5D ⁹⁰	x		x	x		x	x	x	x	
Patient satisfaction	PCBSS ⁹¹			x				x			

Principal Investigator: [name]

Motivation for treatment	SOCRATES ⁷³	X		X				X	
Stigma and Discrimination	Ahern et al. ⁹²	X						X	X
Buprenorphine Diversion	MGH Medication Questionnaire			X	X		X	X	X
Non-study resource utilization	Non-Study Resources Form	X			X		X	X	
Criminal justice resource utilization	Criminal and Legal Activities Form	X			X		X	X	
PTSD symptoms	PCL-5				X		X	X	X
Traumatic reexposure	LEC-5				X		X	X	X
Medical Record Review									
Treatment engagement	-					30 days			
Retention in care	-					3 month, 6 month			

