Aim 1: Secondary outcomes (efficacy): a.) Illicit opioid use: We will check urine drug testing at each research visit and use the Addiction Severity Index (ASI) to assess self-reported substance use.⁸⁷ We have adapted the ASI to also assess use of illicit buprenorphine.¹³ We will report the following continuous measures in each study arm: the percentage of urine drug tests that are positive for illicit opioids (opiates, oxycodone, methadone, illicit buprenorphine), self-reported days of illicit opioid use, and percent of participants achieving *opioid abstinence*, defined as no illicit opioid use based on self-report and urine drug testing.

Principal Investigator: [name]

b.) Retention in treatment: For participants initiating BMT, we will determine whether they are retained in treatment at three and six months following initiation (dichotomous measure). We will define retention as having a medical visit and active buprenorphine prescription each month after BMT initiation. We will also determine the proportion of days following BMT initiation that participants had an active prescription in order to detect lapses in treatment (continuous measure).

c.) HIV risk behaviors: We will determine changes in drug-related HIV risks using the HIV Risk Behavior Survey – a validated, well-studied instrument that documents injection and sexual behaviors over the previous 30 days. This instrument has been studied among out-of-treatment PWID and BMT patients.^{86,93} As previously reported, we will create a dichotomous measure (yes/no) of injecting risk based on self-report of at least one risk behavior (sharing syringes, not using bleach to clean syringes, sharing cookers, or front/back loading of syringes).⁹³ Individual risk behaviors will be explored individually.

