Data management. Urine drug tests will be conducted at the syringe exchange program or CHC and will be entered onto a paper Case Report Form and then entered into a password protected database. The entry will be verified by another staff member. Interviews using REDcap surveys allow for direct data entry by study participants. To ensure confidentiality, participant identifiers will not be recorded on interviews or other data forms. Instead, participants will be assigned a unique study ID that will be used on all data documents and in databases. Participant's names and consent forms will be stored separately from research data in locked file cabinets. Electronic data will be stored in a password-protected server, which will be back up daily and can only be accessed by the research team. Because we will be collecting data on buprenorphine diversion, we also received a Certificate of Confidentiality from NIDA to provide additional protection of confidentiality (see Human Subjects for details).

Analysis: All primary analyses will be intention to treat, including participants who are lost to follow-up. In secondary analyses, we will conduct per-protocol analyses to ascertain outcomes among participants who actually initiate BMT at the SEP or CHC. We will conduct additional exploratory analyses on a per-protocol basis to further assess outcomes (e.g., satisfaction with buprenorphine treatment)

Preliminary analyses. We will first review and summarize data using descriptive summaries and graphical analyses to ensure that reported values are within appropriate ranges, to check for the presence of outliers and abnormal values, and to verify that the distributions of measures meet the assumptions of the statistical tests that are planned as described below.

Missing data. For missing categorical data, we will use multivariate multiple imputation using the fully conditional specification method.¹⁰¹ We will repeat imputations 20 times, and then we will compare statistical results using datasets that include imputed values and the dataset that drops missing values. This will guide our interpretation of our assessment of the impact of missing data on our study findings, as well as our interpretation of overall results.

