- 1) receiving opioid agonist treatment in the past 30 days (confirmed by NY Prescription Drug Monitoring Program);
- 2) inability to provide informed consent
- 3) unstable mental illness (e.g., suicidality, psychosis, etc.)
- 4) severe alcohol use disorder or benzodiazepine use disorder by DSM-V criteria
- 5) hypersensitivity to buprenorphine or naloxone.
- 6) pregnancy (confirmed via urine testing)

Rationale for inclusion/exclusion criteria: Study participants will include out-of-treatment SEP participants with OUD. We will only include participants who are interested in BMT, motivated for OUD treatment, and willing to accept referral to a CHC for treatment, because our goal is to increase engagement in comprehensive BMT. Providing BMT onsite at SEPs could attract participants who are unready to stop illicit opioid use and only want buprenorphine temporarily to reduce withdrawal symptoms or because they do not have access to their illicit opioid of choice. There may be benefits to this type of symptom treatment, but our study is not designed to evaluate these benefits. We will exclude those with clinical contraindications to BMT,

from our own pilot data and several studies that referred SEP participants to MMT. Engagement after passive referral may be as low as 0%,¹⁴ while referral to MMT has resulted in 9-16% of SEP participants engaging in treatment.³⁷⁻³⁹ Therefore, we will recruit a sample of 250, which allowing for up to 20% attrition (n=200), giving us at least 80% power for the primary outcome (**BMT engagement**) in all proposed scenario.

For Aim 2, we chose the intention to treat analysis as the primary outcome. With a sample size of 250 and an expect rate of diversion of 10-25%, we will only have 80% power to declare that diversion rate in the O-BMT arm is non-inferior to the referral arm if the inferiority margin of the risk difference is 10-

Principal Investigator: [name]

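### Retention, a secondary efficacy outcome, is defined only among participants who initiate BMT and timed from initiation; no retention proportion is defined for all randomised participants

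*Combined protocol and SAP*

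**What the plan says.** Under Main outcome variables, Aim 1: Secondary outcomes (efficacy), item b, the population and clock are set together: "For participants initiating BMT, we will determine whether they are retained in treatment at three and six months following initiation". The criterion follows: "We will define retention as having a medical visit and active buprenorphine prescription each month after BMT initiation". A continuous version has the same starting point: "We will also determine the proportion of days following BMT initiation that participants had an active prescription". Table 2 gives the assessment times under Medical Record Review as "3 month, 6 month", without naming an origin.

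The Analysis section states "All primary analyses will be intention to treat, including participants who are lost to follow-up" and places analyses of people who actually start treatment among the secondary, per-protocol analyses. The Aim 1 analysis text gives tests or models for 30-day engagement, opioid use and HIV risk behaviours, but has no hypothesis, test or model for retention.

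The theoretical framework says that onsite treatment "is predicted to increase BMT initiation and engagement".

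Two other places bear on the point. The primary-outcome paragraph also lists three 24-week measures with no restriction to initiators: whether a prescription was filled, total weeks of prescribed treatment, and time to initiation. For diversion (H4), the plan notes that only people with a prescription can divert, yet keeps intention to treat in order to preserve the randomisation.

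**The concern.** Randomisation makes the two arms alike at enrolment. It does not make those who later start treatment alike. In the referral arm a participant must reach a health-centre appointment before starting; in the O-BMT arm treatment starts at the syringe exchange. If O-BMT works as intended, its initiators include people who would not have started under referral. Those people sit in the O-BMT denominator, while their counterparts in the referral arm drop out of the referral denominator.

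Retention is listed as an efficacy outcome in a two-arm trial and is not labelled descriptive, so a comparison of arms is a natural use of it. At stake is a retention result that shows no difference, or an apparent deficit, when more of the people randomised to O-BMT are in treatment at the same time.

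The clock adds a smaller difficulty. Time zero differs between participants, and six months from initiation lies beyond the 24-week follow-up.

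**Working it through.** **The plan's own figure.** No sample size or power is given for retention. Section D.10 covers 30-day engagement: "Therefore, we will recruit a sample of 250, which allowing for up to 20% attrition (n=200), giving us at least 80% power". The hardest pair in Table 3 is 16% against 33%. With two-sided alpha of 5% (assumed, as Aim 1 states none), 80% power and pooled proportion 0.245:

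n per arm = [1.96 × √(2 × 0.245 × 0.755) + 0.842 × √(0.16 × 0.84 + 0.33 × 0.67)]² / 0.17² = 99.3, so 100 per arm and 200 in total. Allowing for attrition, 200/(1 − 0.20) = 250.

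This matches the plan, so the planning rates are read as intended.

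**Illustration: inputs.**
- 125 per arm, from "we will recruit 250 out-of-treatment opioid users from SEPs and randomize 1:1 to onsite BMT initiation" (250/2).
- c = share who would initiate in either arm; t = share who initiate under O-BMT, including everyone in c. Neither is in the documents. Stand-ins are the planning engagement rates in D.10: c = 9-16%, t = 33-68%.
- rA = retention in the first group, the same in both arms; rB = retention in the extra O-BMT initiators. Assumed values are rA = 68% and rB = 68% or 42%. The 68% and 42% are borrowed from the New York City pilot's 3- and 12-month retention, only as two plausible levels.
- Non-initiators count as not retained.

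**Formulas.**
- Initiators only: referral rA; O-BMT [c·rA + (t − c)·rB]/t. Difference = (t − c)(rB − rA)/t.
- All randomised: referral c·rA; O-BMT c·rA + (t − c)·rB. Difference = (t − c)·rB.

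In this model the all-randomised difference is never negative. The sign of the initiators-only difference depends solely on whether the extra initiators do better or worse than the others.

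**Results (referral vs O-BMT, %).**

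| c, t | rB | Initiators only | Difference (points) | All randomised | Difference (points) |
|---|---|---|---|---|---|
| 16%, 33% | 68% | 68.0 vs 68.0 | 0 | 10.9 vs 22.4 | +11.6 |
| 16%, 49% | 68% | 68.0 vs 68.0 | 0 | 10.9 vs 33.3 | +22.4 |
| 9%, 68% | 68% | 68.0 vs 68.0 | 0 | 6.1 vs 46.2 | +40.1 |
| 16%, 33% | 42% | 68.0 vs 54.6 | −13.4 | 10.9 vs 18.0 | +7.1 |
| 16%, 49% | 42% | 68.0 vs 50.5 | −17.5 | 10.9 vs 24.7 | +13.9 |
| 9%, 68% | 42% | 68.0 vs 45.4 | −22.6 | 6.1 vs 30.9 | +24.8 |

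The fifth row in full: 0.16 × 0.68 = 0.1088; 0.33 × 0.42 = 0.1386; the sum is 0.2474; 0.2474/0.49 = 0.505. The initiators-only comparison there would rest on 125 × 0.16 = 20 people against 125 × 0.49 ≈ 61.

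**When does the sign flip?** Without the rA/rB model, the two differences have opposite signs whenever the ratio of O-BMT to referral initiator retention lies between c/t and 1. The lower limit is 0.16/0.33 = 0.485, 0.16/0.49 = 0.327 or 0.09/0.68 = 0.132. If the extra initiators are retained better than the others (rB above rA), there is no flip. The initiators-only gain is then smaller than the all-randomised gain as long as rB is below rA/(1 − t). With rA = 0.68 and t of at least 0.33 that limit is at least 0.68/0.67, above 1, so it always holds here. If referral initiation were 0%, there would be nobody to compare.

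**Timing.** Six months is about 182.6/7 = 26.1 weeks. Even someone who starts on the day of randomisation reaches that point after week 24, and later starters reach it later.

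**The case against.** **No between-arm retention test is planned.** This is correct. A reader might infer that the plan commits itself to a biased comparison; the documents do not say that. They list retention as an efficacy outcome, leave its comparison unspecified, and do not label it descriptive. The gap is real, but it is one of definition.

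**Other measures cover treatment exposure.** The three unrestricted 24-week measures and the intention-to-treat primary outcome would sit beside any odd retention figure. That softens the consequence. Total weeks prescribed is cumulative, however. It does not show how many randomised people are still attending and prescribed at a given time.

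**The planning rates are not initiation rates.** This stands. The 68% is three-month retention in one pilot; the 33% is 3 of 9 people transferred, although 7 of 9 completed the onsite course; the 49% is transition to primary care. The referral figures come from passive referral (0%) and referral to methadone treatment (9-16%), not from enhanced referral with an appointment within a week. Eligibility also requires interest and motivation in both arms, which narrows any difference between early and extra initiators. A reader might infer that reversal is to be expected; nothing in the documents shows that.

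**Six-month data may exist.** This also stands. Retention comes from medical and prescription-monitoring records extracted at study completion, not from research visits. The sentence ruling out measurements after 24 weeks is in the economic section, where it explains why costs are not discounted. A reader might infer that the six-month point cannot be observed; the documents do not establish this. They leave the extraction window unstated.

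**Conclusion.** The point holds as a gap in one secondary efficacy outcome. Retention has no all-randomised version, and the defined version conditions on an event that the intervention is designed to change. The plan's handling of diversion shows that it recognises the same problem elsewhere and resolves it by keeping everyone randomised.

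The size cannot be fixed from the documents. Under the assumed rates, equal retention in all initiators hides an all-randomised gain of 11.6 to 40.1 points behind a difference of zero. If the extra initiators are retained at 42% rather than 68%, an all-randomised gain of 7.1 to 24.8 points appears as a deficit of 13.4 to 22.6 points. The algebra is general within the model; the numbers are illustrative. They rest on engagement standing in for initiation, on borrowed retention levels, and on O-BMT not changing retention in those who would start anyway.

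The 30-day primary outcome and its power are untouched. The definition should be amended before analysis, with moderate priority.

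**What to change.** 1. Define retention for all randomised participants as a medical visit plus an active prescription at weeks 12 and 24 after randomisation, and state the look-back window for each. Count non-initiators as not retained, and say that they are not to be treated as missing under the multiple-imputation rule.
2. Name this as the measure for the between-arm comparison, by intention to treat, and add its test or model to the Aim 1 analysis text.
3. Keep the three- and six-month initiators-only proportions and the proportion of days covered as within-arm description, with no between-arm test.
4. Reconcile the six-month-from-initiation time point with the 24-week follow-up by stating how far the record extraction runs, and give the time origin in Table 2.

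The cost is small: revised wording and a little extra analysis of records already being extracted. The state prescription database covers dispensing for everyone randomised. Visits outside the community health center still depend on the signed record releases already planned.
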